9.4.3.3 Action Taken with Study Drug

Action taken with Study Drug due to the event is characterized by the following.

- **None:** No changes were made to Study Drug administration and dose
- **Permanently Discontinued:** Study Drug was discontinued and not restarted
- **Temporarily Interrupted, restarted:** Dosing was temporarily interrupted or delayed due to the AE and restarted

- **Reduced dose:** Dosing was reduced to a lower dose
- **Reduced schedule:** Dosing frequency was reduced

9.4.3.4 Treatment Given for Adverse Event

Any treatment (e.g., medications or procedures) given for the AE should be recorded on the Adverse Event Case Report Form (treatment should also be recorded on the concomitant treatment or ancillary procedures CRF as appropriate).

9.4.3.5 Outcome of the Adverse Event

If the event is a non-serious AE then the event's outcome is characterized by 1 of the following:

- **AE Persists:** Patient terminates from the trial and the AE continues
- **Recovered:** Patient recovered completely from the AE
- **Became Serious:** The event became serious (the date that the event became serious should be recorded as the Resolution Date of that AE and the Onset Date of the corresponding SAE)
- **Change in Severity (if applicable):** AE severity changed

If the event is a SAE then the event's outcome is characterized by 1 of the following:

- **Ongoing:** SAE continuing
- **Persists (as non-serious AE):** Patient has not fully recovered but the event no longer meets serious criteria and should be captured as an AE on the non-serious AE eCRF (the SAE resolution date should be entered as the date of onset of that AE)
- **Recovered:** Patient recovered completely from the SAE (the date of recovery should be entered as the SAE resolution date)
- **Fatal:** Patient died (the date of death should be entered as the SAE resolution date)

9.5 Procedures for Handling Special Situations

9.5.1 Abnormalities of Laboratory Tests

Clinically-significant abnormal laboratory test results may, in the opinion of the Investigator, constitute or be associated with an AE. Examples of these include abnormal laboratory results that are associated with symptoms, or require treatment, e.g., bleeding due to thrombocytopenia, tetany due to hypocalcemia, or cardiac arrhythmias due to hyperkalemia. Whenever possible, the underlying diagnosis should be listed in preference to abnormal laboratory values as AEs.

Clinically-significant abnormalities will be monitored by the Investigator until the parameter returns to its baseline value or until agreement is reached between the Investigator and the Study Medical Monitor. Laboratory abnormalities deemed not clinically-significant (NCS) by the Investigator should not be reported as AEs. Similarly, laboratory abnormalities reported as AEs by the Investigator should not be deemed NCS on the laboratory sheet.

The Investigator is responsible for reviewing and signing all laboratory reports. The signed clinical laboratory reports will serve as source documents.

9.5.2 Prescheduled or Elective Procedures or Routinely Scheduled Treatments

A prescheduled or elective procedure or a routinely scheduled treatment will not be considered an SAE, even if the patient is hospitalized; the Study Center must document all of the following:

- The prescheduled or elective procedure or routinely scheduled treatment was scheduled (or was on a waiting list to be scheduled) prior to obtaining the patient's consent to participate in the study
- The condition that required the prescheduled or elective procedure or routinely scheduled treatment was present before and did not worsen or progress in the opinion of the Investigator between the patient's consent to participate in the study and the timing of the procedure or treatment
- The prescheduled or elective procedure or routinely scheduled treatment is the sole reason for the intervention or hospital admission

9.5.3 Dosing Errors

Study medication errors should be documented as Protocol Deviations. A brief description should be provided in the deviation, including whether the patient was symptomatic (list symptoms) or asymptomatic, and the event accidental or intentional.

Dosing details should be captured on the Dosing Case Report Form. If the patient takes a dose of Study Drug that exceeds protocol specifications and the patient is symptomatic, then the symptom(s) should be documented as an AE and be reported per Section 9.4.

Should an overdose occur, the Investigator or designee should refer to the Guidance to Investigator's section of the Investigator's Brochure and contact the Sponsor or designee within 24 hours.

9.5.4 Contraception and Pregnancy

Male patients and female patients of childbearing potential must continue to use appropriate contraception with their partners, or refrain from sexual activity, as described in Section 6.3.1.

If a patient becomes pregnant or a pregnancy is suspected, or if a male patient makes or believes that he has made someone pregnant during the study, then the Study Center staff must be informed immediately. An Initial Pregnancy Form should be submitted to the Sponsor or designee **within 24 hours** of first learning of the occurrence of pregnancy. Follow-up information including delivery or termination is reported on Follow-up Pregnancy Forms and reported within 24 hours.

Payment for all aspects of obstetrical care, child or related care will be the patient's responsibility.

Female patients: If a suspected pregnancy occurs while on the study (including follow-up), a pregnancy test will be performed. The patient with a confirmed pregnancy will be immediately

withdrawn from treatment with Study Drug. However, the patient will be encouraged to complete the post-treatment follow-up portion of the study to the extent that study procedures do not interfere with the pregnancy. Regardless of continued study participation, the study physician will assist the patient in getting obstetrical care and the progress of the pregnancy will be followed until the outcome of the pregnancy is known (i.e., delivery, elective termination, or spontaneous abortion). If the pregnancy results in the birth of a child, the Study Center and Sponsor may require access to the mother and infant's medical records for an additional 8 weeks after birth.

Male patients: The progress of the pregnancy in a male patient's partner should be followed until the outcome of the pregnancy is known (i.e., delivery, elective termination, or spontaneous abortion). If the pregnancy results in the birth of a child, additional follow-up information may be requested for the mother and infant. Follow-up will be performed to the extent permitted by applicable regulations and privacy considerations.

10. STATISTICAL CONSIDERATIONS

10.1 Study Endpoints, Subsets, and Covariates

10.1.1 Primary Endpoints

The primary endpoints are the change in mNIS+7 score from baseline to Week 66 and the change in the Norfolk QOL-DN questionnaire total score from baseline to Week 66.

10.1.2 Secondary Endpoints

10.1.2.1 Secondary Efficacy Endpoints

- Change in the Norfolk QOL-DN questionnaire symptoms domain score (Stage 1 patients only) and Norfolk QOL-DN questionnaire physical functioning/large fiber neuropathy domain score (Stage 2 patients only) from baseline to Week 66
- Change in the mBMI and BMI from baseline to Week 65
- Change in NIS and modified +7 from baseline to Week 66
- Change in NIS +7 score from baseline to Week 66
- Change in GLS by ECHO from baseline to Week 65 in the ECHO subgroup and in the CM-ECHO Set

10.1.2.2 Pharmacodynamic Endpoint

- Change from baseline in TTR level to Week 65
- Change from baseline in RBP4 level to Week 65

10.1.2.3 Safety Endpoints

- Adverse events
- Vital signs and weight
- Physical examination
- Clinical laboratory tests
- ECG
- Use of concomitant medication
- Ophthalmology and ERG examinations
- Columbia-Suicide Severity Rating Scale
- Thyroid panel
- Inflammatory panel
- Coagulation
- Complement
- Immunogenicity

10.1.2.4 Pharmacokinetic Endpoints

Selected ISIS 420915 post-distribution plasma concentrations (i.e., trough and various post-treatment time points) will be measured throughout the study and the estimated plasma terminal elimination half-life ($t_{1/2\lambda_z}$) after end of treatment will be calculated (when possible). In evaluable patients from the PK subgroup, additional selected plasma PK parameters (as outlined in Section 10.5.4) will also be determined after dosing on Days 1, 240, and 449. Further details of the various planned plasma PK assessments are outlined in Section 10.5.4.

10.1.3 Tertiary Endpoint

- Change from baseline to Week 65 in SF-36 questionnaire domain scores
- Change from baseline to Week 66 in the individual components of the NIS (cranial, muscle weakness, reflexes and sensory), modified +7 (heart rate to deep breathing, nerve conduction, heat-pain sensory and touch-pressure sensory testing), and +7 (vibration detection threshold and nerve conduction)
- Change from baseline to Week 66 in +7
- Change from baseline to Week 66 in individual domain scores of Norfolk QOL-DN (physical functioning/large fiber neuropathy, symptoms, activities of daily living, small fiber neuropathy and autonomic neuropathy)

10.1.4 Exploratory Endpoints

- Change from baseline in echocardiogram parameters (except GLS) in the ECHO subgroup and in the CM-ECHO Set
- Change from baseline in NT-proBNP
- Change from baseline in the PND score
- Change from baseline in the NSC score
- Change from baseline in retinol
- Change from baseline in retinyl palmitate

10.2 Sample Size Considerations

The sample size for this study was estimated using information published from the placebo controlled Phase 3 Diflunisal trial (Berk et al. 2013), a retrospective, multinational natural history study in 283 FAP patients (Adams et al. 2015), and uncontrolled data using another TTR mRNA targeted therapeutic (Adams 2015). It is estimated that the placebo group will have a 16 point increase in the mNIS+7 score from baseline to Month 15, and the treated group will have a 6.4 point increase in mNIS+7. The standard deviation of the change from baseline in each treatment group is estimated to be 14. With 135 patients (2:1 allocation ratio) there would be at least 90% power to detect a 9.6 point difference in the change from baseline in the mNIS+7 score between the 2 groups, with a 2-sided t-test of 5% alpha, assuming that the dropout rate is approximately 25%.

For the Norfolk QOL-DN questionnaire total score, it is estimated that the placebo group will have a 13.3 point change from baseline to Month 15, the treated group will have a 2.6 point change from baseline and the standard deviation of the change from baseline in each treatment group will be 18. With 135 patients, there would be at least 80% power to detect a 10.7 point difference in the change from baseline in the Norfolk QOL total score between the 2 groups, with a 2-sided 5% alpha, assuming that the dropout rate is approximately 25%.

10.3 Populations

The Full Analysis Set will include all randomized patients who received at least 1 injection of Study Drug (ISIS 420915 or placebo) and who have at least 1 post-baseline efficacy assessment for the mNIS+7 score or Norfolk QOL-DN questionnaire total score.

The Safety Set will include all randomized patients who received at least 1 injection of Study Drug.

The Per-Protocol Set will include the subset of the Full Analysis Set that have received at least a certain percentage of the prescribed doses of Study Drug and that have no significant protocol deviations that would be expected to affect efficacy assessments. The detailed criteria will be specified and finalized prior to conducting the primary analysis (i.e., exact criteria to determine inclusion in or exclusion from the Per Protocol Set will be determined for each patient prior to conducting the primary analysis).

The Pharmacokinetic Set will include the subset of the Safety Set that has at least 1 evaluable PK result.

The ECHO subgroup will include the subset of the Safety Set that has at least 1 evaluable post baseline ECHO assessment and participated in the ECHO substudy. The CM-ECHO Set will include the subset of the Safety Set that has at least 1 evaluable post baseline ECHO assessment and had a diagnosis of TTR cardiomyopathy at study entry but are not in the ECHO subgroup, plus patients who participated in the ECHO subgroup.

10.4 Interim Analysis

A pharmacodynamic interim analysis of reduction in plasma TTR level will be performed by the independent statistician and reviewed by the DSMB after approximately 45 patients have completed the Week 13 visit. This interim will be a futility analysis, so there will be no statistical penalty assigned. The results of this interim analysis will result in a decision to continue the study as planned or to stop the study. Details of the analysis and controlled access to the unblinded data are outlined in the SAP and DSMB Charter.

10.5 Planned Methods of Analysis

All eCRF data, lab data transfers, mNIS+7 score data, as well as any outcomes derived from the data, will be provided in the patient data listings. Patient data listings will be presented for all patients enrolled into the study.

Descriptive summary statistics including n, mean, median, standard deviation, interquartile range (25th percentile, 75th percentile), and range (minimum, maximum) for continuous variables, and counts and percentages for categorical variables will be used to summarize most data by treatment group. Where appropriate, p-values will be reported. All statistical tests will be conducted using 2-sided tests with 5% Type I error rates unless otherwise stated.

All primary, secondary and tertiary efficacy and pharmacodynamic endpoints, except GLS will be assessed on the Full Analysis Set and Per-Protocol Set, with the former being the basis for the primary efficacy analysis. All safety assessments will be performed on the Safety Set. PK endpoints will be assessed in the PK Set as applicable. ECHO endpoints including GLS will be assessed in the ECHO subgroup and in the CM-ECHO Set.

10.5.1 Demographic and Baseline Characteristics

Demographic and baseline characteristics will be summarized using descriptive statistics by treatment group. All patients enrolled will be included in a summary of patient disposition.

10.5.2 Safety Analysis

Treatment duration and amount of Study Drug received will be summarized by treatment group, as well as reasons for withdrawal from Study Drug.

All treatment-emergent adverse events (AEs with onset after the first dose of Study Drug) and serious adverse events will be summarized for each treatment group using the MedDRATM coding system, by system organ class, preferred term, relationship to Study Drug, and severity. Narratives of deaths, serious adverse events, including early withdrawals from Study Drug and from study due to adverse events, will also be provided.

Laboratory tests to ensure patient safety including chemistry panel, complete blood count with differential, coagulation panel, and complement, will be summarized by study visits for each treatment group. These safety variables will also be presented as change and percent change from baseline over time after Study Drug administration, as appropriate.

Vital sign, weight, and ECG measures will be summarized by treatment group. In addition, the number of patients who experience abnormalities in clinical laboratory evaluations will be summarized by treatment group.

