3.2.1.4 Data Summary Plan

The table below details what data will be included in the summary and analysis output by endpoint type, and what output is planned for the EOT and what output will be updated for the EOS. Data summarized/analyzed at EOT will be based on data collected up to the date of the data cut. It is possible that the on-treatment set of data available at EOS will be different to the one that was available at EOT because data collected after the EOT data cut may slot into the on-treatment period. On-treatment output provided at the EOT will be updated at EOS if the data in the on-treatment period has changed from EOT. In select instances the data for a type of endpoint that is summarized or analyzed may not be consistent with the rules in the Table; such exceptions will be noted in this document. Note: assessments for mNIS+7, NSC, ERG, and ophthalmology done early in the treatment period that are used for baseline cannot also be used as an on-treatment assessment.

Endpoint type	Provide at EOT	Update at EOS	Comment/definition
Efficacy	-Listings -On-treatment summary/analysis tables -Post-treatment summary tables	-Listings -On-treatment summary/analysis tables -Post-treatment summary tables	-On-treatment: First dose date \leq Date of assessment \leq Last dose date + 52 days -Post-treatment: Date of assessment $>$ last dose date + 52 days -Visit defined by analysis visit window -The primary inference for mNIS+7 and Norfolk QOL-DN will be made at EOT, even if data slotted in the on-treatment period has changed by EOS
PD, BMI and mBMI, ERG	-Listings -On-treatment summary/analysis tables -Post-treatment summary tables	-Listings -On-treatment summary/analysis tables -Post-treatment summary tables	-On-treatment: First dose date \leq Date of assessment \leq Last dose date + 28 days -Post-treatment: Date of assessment $>$ last dose date + 28 days -Visit defined by analysis visit window
ECG, Lab, vital signs (including body weight),	-Listings -On-treatment summary tables -Post-treatment summary tables	-Listings -On-treatment summary tables -Post-treatment summary tables	-On-treatment: First dose date \leq Date of assessment \leq Last dose date + 7 days -Post-treatment: Date of assessment $>$ last dose date + 7 days -Visit defined by analysis visit window -Abnormal lab analyses described in Sections 3.9.4.1 to 3.9.4.3 include post-baseline data

Endpoint type	Provide at EOT	Update at EOS	Comment/definition

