3.9.4 Laboratory Measurements

Laboratory tests to ensure patient safety include chemistry panel, complete blood count with differential, thyroid panel, coagulation panel, immunogenicity, inflammatory panel, complement, and urinalysis. Absolute values, change and percent change from baseline will be summarized by visit and treatment group for continuous laboratory tests. No statistical comparisons between treatments will be conducted for these summaries. The mean value (and associated standard error) will be plotted by treatment group over visits for the following laboratory parameters: platelets, eGFR, urine A/C ratio, and urine P/C ratio.

All laboratory test results will be listed. Separate listings will be provided for local and central labs. The central lab listing will be based on the ADaM dataset and will include all central lab records. The local lab listing will be based on the SDTM dataset. A separate listing for platelets will be provided that includes assessment from both the local and central labs. A separate listing will contain only values outside of normal ranges. The number and percent of patients that stopped treatment because they met a protocol-defined stopping rules for liver function, renal function, or platelet counts will be tabulated by treatment group.

Additional investigation of hepatobiliary laboratory assessments, platelet counts and renal parameters will be performed, and are detailed in the sections below. In this investigation confirmed laboratory values will also be summarized.

A confirmed laboratory value is based on consecutive lab values within 7 days. If that value is in the same or worse category the initial value is confirmed. If the consecutive value is in a better category then the initial value is confirmed using consecutive value category. If there is no retest within 7 days then the initial value is presumed confirmed. If there are multiple results on the same day (no matter from the same lab vendor or different lab vendors), then the worst value will be utilized in the analysis.

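### Protocol 10.5.2 promises counts by arm of patients with laboratory abnormalities; the SAP specifies counts from laboratory values only for liver, platelets and kidney, and does not flag the restriction

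*Protocol*

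**What the plan says.** Protocol 10.5.2 makes two laboratory commitments. The first is a visit-by-visit summary: "Laboratory tests to ensure patient safety including chemistry panel, complete blood count with differential, coagulation panel, and complement, will be summarized by study visits". The second is a patient-level count: "the number of patients who experience abnormalities in clinical laboratory evaluations will be summarized by treatment group". The second names no organ system, no analyte and no threshold.

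SAP 3.9.4 carries out the first commitment: "Absolute values, change and percent change from baseline will be summarized by visit and treatment group for continuous laboratory tests". On values outside the reference range it says: "A separate listing will contain only values outside of normal ranges". It then narrows the patient-level work to three areas: "Additional investigation of hepatobiliary laboratory assessments, platelet counts and renal parameters will be performed, and are detailed in the sections below". Those sections (3.9.4.1 to 3.9.4.3) give the number and percentage of patients per category for liver tests, platelets and renal parameters. The data summary plan in SAP 3.2.1.4 describes the same scope: "Abnormal lab analyses described in Sections 3.9.4.1 to 3.9.4.3 include post-baseline data". The tabulation of patients who stopped treatment under a laboratory rule is limited in the same way: "stopping rules for liver function, renal function, or platelet counts will be tabulated by treatment group".

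**The concern.** A count of patients per arm who crossed a limit answers a different question from a visit summary or a listing. A visit summary gives location, spread and one extreme at each end. A listing gives individual values with no denominator and no comparison. Neither tells the reader how many patients on ISIS 420915, and how many on placebo, went from normal to abnormal on a given test.

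This matters here because protocol 2.3.3 names transient complement activation and acute aPTT elevation as class effects seen in the monkey, and protocol 10.1.2.3 lists coagulation, complement, thyroid and inflammatory panels among the safety endpoints. If the counts are not specified before unblinding, any added later will use thresholds chosen with the data in view.

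**Working it through.** No arithmetic applies, since the point rests on no sample size, error rate or power figure. The check sets the protocol sentence against what the SAP specifies for each test group (analytes from protocol Appendix B).

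| Test group | Within the 10.5.2 sentence? | Count by arm from laboratory values in the SAP | Other SAP output |
|---|---|---|---|
| ALT, AST, total bilirubin, ALP | Yes | Yes, 3.9.4.1 | Visit summary, listing |
| Platelets | Yes | Yes, 3.9.4.2 | Visit summary, listing |
| Serum creatinine, CKD-EPI clearance, urine Alb/C and P/C | Yes | Yes, 3.9.4.3 | Visit summary, listing |
| Haemoglobin, white cells, differential | Yes | None | Visit summary, listing |
| Remaining chemistry (e.g. electrolytes, creatine kinase, IgG, IgM) | Yes | None | Visit summary, listing |
| PT, aPTT, INR | Yes by grouping in 10.5.2, though a separate endpoint in 10.1.2.3 | INR > 1.5 only jointly with ALT or AST >= 3xULN | Visit summary, listing, AE table (Coagulopathies HLT) |
| C3, C5a, Bb | As for coagulation | None | Visit summary, listing, AE table (Hypersensitivity SMQ) |
| TSH, FT4 | Less clear | None | Visit summary, listing, AE table (Hypothyroidism SMQ) |
| hsCRP | Less clear | None | Visit summary, listing |
| Retinol | Less clear: exploratory in protocol 10.1.4, moved to safety laboratory parameters in SAP 3.6 | None | Visit summary, listing, AE table (ocular events related to vitamin A deficiency) |

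Three further checks:

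1. **Could the AE tables stand in for the counts?** They depend on what investigators report, and protocol 9.5.1 says: "Laboratory abnormalities deemed not clinically-significant (NCS) by the Investigator should not be reported as AEs". In addition, SAP 2.5.2 withholds post-treatment retinol and hsCRP results from investigators until the end-of-treatment lock, so those central results cannot prompt an AE report during blinded treatment.

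2. **Is a count implied elsewhere?** SAP 3.2.1.3 says safety values not used in the visit tables will still feed into the identification of treatment-emergent shifts or abnormalities. That suggests more than a listing was intended, but no table, threshold or shift category is defined for the groups marked None. The visit tables take the value nearest the target day, so another abnormal value in the same window would appear only in a listing.

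3. **Is the restriction declared?** The SAP notes other departures from the protocol: tertiary endpoints not analysed in the Per-Protocol Set (3.2.1 and 3.5) and retinol reclassified (3.6). It does not note this one.

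**The case against.** The best case for the plan has four parts.

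**Scope.** The protocol synopsis describes clinical laboratory parameters as including haematology, serum chemistry and urinalysis, and 10.1.2.3 lists thyroid, inflammatory, coagulation and complement panels separately from clinical laboratory tests. The promise may therefore be narrower than it looks. This stands in part. It leaves thyroid, hsCRP and retinol uncertain. It does not remove haemoglobin, white cells or the remaining chemistry, and 10.5.2 itself puts coagulation and complement with the safety laboratory tests.

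**Existing output.** A reader might infer that abnormalities in these panels are counted nowhere, or that the visit tables would conceal them. The documents do not support either reading. SAP 3.9.2.1 and 3.9.2.2 tabulate related AE categories by arm, and 3.9.2 adds risk differences with 95% CIs. SAP 3.2.1 includes minimum and maximum in the descriptive statistics, so one extreme value at a summarised visit would be visible. What remains absent is the number of patients beyond a limit.

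**Frequency and sampling.** A reader might also infer that the effects at stake are confined to a few patients, whom only a count would reveal. Protocol 2.3.4 points the other way for two tests: in Phase 1, C-reactive protein rose in nearly all subjects at multiple doses of 200 mg or more, and retinol fell below LLN in about 50% of multiple-dose subjects. For the acute class effects, Appendix A samples PT, aPTT, INR and C3 before dosing in the full population. Post-dose coagulation, and C5a and Bb at any time, are collected only in the PK subgroup of about 20. A full-population count would largely miss an acute post-dose change. This stands and shapes the fix.

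**Urinalysis.** A reader might infer that categorical dipstick results get no summary, because 3.9.4 speaks of continuous tests. SAP 3.2.1 sets counts and percentages for categorical variables as a general convention, so that reading is not secure.

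**Conclusion.** The point holds in a limited form. The SAP as written does not produce the patient counts by arm promised in protocol 10.5.2 for haemoglobin, white cells and the remaining chemistry, nor, on the natural reading of that section, for coagulation and complement. It does so in part, for liver, platelets and kidney. Whether thyroid, hsCRP and retinol are covered is open to interpretation.

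It would go too far to say that 10.5.2 requires an LLN/ULN rule, a restriction to patients normal at baseline, or a shift table, because the section names none of these.

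The issue is minor. The primary and secondary efficacy inferences are unaffected, every value is collected, and out-of-range values are listed. The loss is one comparison by arm that the protocol names, together with the protection of having its criteria fixed before unblinding. The conclusion assumes that SAP 3.9.4 and its subsections are the full specification of laboratory tables, which SAP 3.2.1.4 supports.

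**What to change.** Before unblinding, add to SAP 3.9.4, for the remaining haematology, chemistry, coagulation and complement analytes, the number and percent of patients per arm with a treatment-emergent value below LLN or above ULN. A baseline-to-worst shift table (low, normal, high) would serve equally well. Include thyroid, hsCRP and retinol as well, preferably, since their place under 10.5.2 is unclear. Use the same post-baseline period as 3.9.4.1 to 3.9.4.3, and include unscheduled central results. Report C5a, Bb and post-dose coagulation in the PK subgroup with that subgroup's denominator. The LLN/ULN rule is one reasonable way to implement the protocol sentence, so the SAP should state it as the chosen rule.

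If the sponsor prefers to keep the counts to liver, platelets and kidney, the SAP should say that this departs from protocol 10.5.2 and give the reason, as it does for its other departures.

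The cost is SAP wording and additional tables programmed from data already collected. The out-of-range listing already requires reference ranges. The downside is a longer safety output.
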